10.4.3. Collection of Pregnancy Information

10.4.3.1. Male Participants with Partners Who Become Pregnant

The Investigator will attempt to collect pregnancy information on any male participant's female partner who becomes pregnant while the male participant is in this study. This applies only to male participants who receive DCR-AUD.

After obtaining the necessary signed informed consent from the pregnant female partner directly, the Investigator will record pregnancy information on the appropriate form and submit it to the Sponsor within 24 hours of learning of the partner's pregnancy. The female partner will also be followed to determine the outcome of the pregnancy. Information on the status of the mother and

child will be forwarded to the Sponsor. Generally, the follow-up will be no longer than 6 to 10 weeks following the estimated delivery date. Any termination of the pregnancy will be reported regardless of fetal status (presence or absence of anomalies) or indication for the procedure.

10.4.3.2. Participants Who Become Pregnant

The Investigator will collect pregnancy information on any participant who becomes pregnant while participating in this study. The initial Information will be recorded on the appropriate form and submitted to the Sponsor within 24 hours of learning of a participant's pregnancy.

The participant will be followed to determine the outcome of the pregnancy. The Investigator will collect follow-up information on the participant and the neonate, and the information will be forwarded to the Sponsor. Generally, follow-up will not be required for longer than 6 to 10 weeks beyond the estimated delivery date. Any termination of pregnancy will be reported, regardless of fetal status (presence or absence of anomalies) or indication for the procedure.

While pregnancy itself is not considered to be an AE or SAE, any pregnancy complication or elective termination of a pregnancy for medical reasons will be reported as an AE or SAE. A spontaneous abortion (occurring at < 22 weeks gestational age) or still birth (occurring at > 22 weeks gestational age) is always considered to be an SAE and will be reported as such. Any post-study pregnancy-related SAE considered reasonably related to the study intervention by the Investigator will be reported to the Sponsor as described in Section 8.3.4. While the Investigator is not obligated to actively seek this information in former study participants, he or she may learn of an SAE through spontaneous reporting.

Any participant who becomes pregnant while participating in the study will discontinue study intervention.

10.5. Genetics

Use/Analysis of DNA

- DNA samples will be analyzed for *ALDH2* genotyping. Additional exploratory analyses may be conducted if it is hypothesized that this may help further understand the clinical data.
- The results of genetic analyses may be reported in the CSR or in a separate study summary.
- The Sponsor will store the DNA samples in a secure storage space with adequate measures to protect confidentiality.
- The samples will be retained while research on DCR-AUD continues, but no longer than 5 years or other period as per local requirements.

10.6. Liver Safety: Suggested Actions and Follow-up Assessments

Phase 1 liver chemistry stopping criteria are designed to ensure participant safety and to evaluate liver event etiology:

Liver Chemistry Stopping Criteria (Applies both to additional DCR-AUD dosing and further EIAs)	
ALT/AST-absolute	
ALT or AST increases to $\geq 3 \times \text{ULN}$
 
If ALT or AST \geq increases to $>2 \times \text{ULN}$ AND total bilirubin $\geq 2 \times \text{ULN}$ ($> 35\%$ direct bilirubin) or INR > 1.5, report to Sponsor in expedited manner.^{a, b}
 
See additional actions and follow-up assessments below

^a Serum bilirubin fractionation should be performed if testing is available. If serum bilirubin fractionation is not immediately available, discontinue study intervention if ALT $\geq 3 \times \text{ULN}$ and total bilirubin $\geq 2 \times \text{ULN}$.

Additionally, if serum bilirubin fractionation testing is unavailable, record the absence/presence of detectable urinary bilirubin on dipstick which is indicative of direct bilirubin elevations suggesting liver injury.

^b All events of ALT $\geq 3 \times \text{ULN}$ and total bilirubin $\geq 2 \times \text{ULN}$ ($> 35\%$ direct bilirubin) or ALT $\geq 3 \times \text{ULN}$ and INR > 1.5 may indicate severe liver injury (possible 'Hy's Law') and must be reported to sponsor in an expedited manner and as an SAE if SAE criteria met (excluding studies of hepatic impairment or cirrhosis).

Required Actions, Monitoring, and Follow-up Assessments	
Actions:	
 Immediately discontinue study intervention Report the event to the CRO Medical Monitor within 24 hours Complete an SAE data collection tool if the event also met the criteria for an SAE^b Perform liver function follow-up assessments as described in the Follow Up Assessments below. Do not restart or rechallenge participant with study intervention (neither IMP nor additional EIAs). Monitor the participant until liver function test abnormalities resolve, stabilize, or return to baseline (as detailed below).
Monitoring:	
If ALT or AST $\geq 3 \times \text{ULN}$ AND total bilirubin $\geq 2 \times \text{ULN}$ or INR > 1.5:
 
 Repeat liver function tests (include ALT, AST, alkaline phosphatase, total bilirubin, and INR) and perform liver function follow-up assessments within 24 hours. Monitor participant twice weekly until liver function test abnormalities resolve, stabilize, or return to baseline. A specialist or hepatology consultation is recommended. 
If ALT or AST $\geq 3 \times \text{ULN}$ AND total bilirubin $< 2 \times \text{ULN}$ and INR ≤ 1.5:
 
 Perform liver function tests (include ALT, AST, alkaline phosphatase, total bilirubin, and INR) and perform liver function follow-up assessments within 24 to 72 hours Monitor participants weekly until liver function abnormalities resolve, stabilize, or return to baseline

Follow-Up Assessments:

- Viral hepatitis serology (includes Hepatitis A IgM antibody; HBsAg and HBcAb; hepatitis C RNA; cytomegalovirus IgM antibody; Epstein-Barr viral capsid antigen IgM antibody [or if unavailable, heterophile antibody or monospot testing]; and hepatitis E IgM antibody)
- Obtain serum CK, LDH, GGT, GLDH, and serum albumin
- Fractionate bilirubin, if total bilirubin $\geq 2 \times \text{ULN}$
- Obtain complete blood count with differential to assess eosinophilia
- Record the appearance or worsening of clinical symptoms of liver injury, or hypersensitivity, on the eCRF
- Record use of concomitant medications or ingestions (including wild mushrooms, acetaminophen, herbal remedies, recreational drugs, and other over-the-counter medications). Note any concomitant medications that have been recently initiated or for which doses have increased.
- Record alcohol use on the eCRF

If ALT or AST $\geq 3 \times \text{ULN}$ AND total bilirubin $\geq 2 \times \text{ULN}$ or INR > 1.5 obtain the following in addition to the assessments listed above:

- Anti-nuclear antibody, anti-smooth muscle antibody, Type 1 anti-liver kidney microsomal antibodies, and quantitative total immunoglobulin G (IgG) or gamma globulins
- Liver imaging (ultrasound, magnetic resonance, or computerized tomography) and/or liver biopsy to evaluate liver disease
- Liver biopsy may be considered and discussed with local specialists if available, for instance:
 - When serology raises the possibility of autoimmune hepatitis (AIH)
 - When suspected DILI progresses or fails to resolve on withdrawal of study intervention
 - In participants with acute or chronic atypical presentation.

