7.3.2. Abnormal Liver Function Tests

Discontinuation of study intervention is required when a participant meets one of the conditions outlined in [Section 10.6](#). Discontinuation of study intervention may also be considered in the presence of other abnormal liver function tests, if the Investigator believes that it is in best interest of the participant.

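### Protocol Section 10.6 sets its combined liver criterion at ALT or AST above 2×ULN but its footnotes, monitoring tiers and extended work-up at 3×ULN or more, so mandatory stopping and monitoring frequency are unsettled between 2 and 3×ULN

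*Protocol*

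**What the plan says.** Protocol Section 10.6 opens with a box headed "Liver Chemistry Stopping Criteria (Applies both to additional DCR-AUD dosing and further EIAs"). It has two lines:

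- **Aminotransferase alone:** ALT or AST at or above 3×ULN.
- **Combined:** ALT or AST above 2×ULN together with either total bilirubin at or above 2×ULN (direct fraction over 35%) or a raised INR. This line ends "or INR > 1.5, report to Sponsor in expedited manner" and says nothing about dosing or EIAs.

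Footnotes a and b are both attached to the combined line and both use ALT at or above 3×ULN. Footnote a calls for discontinuation at that level with bilirubin at or above 2×ULN when fractionation is not immediately available. Footnote b describes possible Hy's Law events, which "must be reported to sponsor in an expedited manner and as an SAE if SAE criteria met".

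The Actions row below the box gives no aminotransferase threshold. It requires immediate discontinuation, notice to the CRO Medical Monitor within 24 hours, the follow-up assessments, no rechallenge with drug or EIA, and monitoring until the abnormality settles, with the detail left to the rows beneath. Those rows hold two monitoring tiers, both starting at ALT or AST at or above 3×ULN. The upper tier includes "Monitor participant twice weekly until liver function test abnormalities resolve, stabilize, or return to baseline". The extended work-up starts at the same level.

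Section 7.3.2 makes the box binding: "Discontinuation of study intervention is required when a participant meets one of the conditions outlined in" Section 10.6.

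**The concern.** A stopping rule should give one answer for one set of results. Here the combined line stands under a stopping heading, states only a reporting duty, and carries footnotes with a different threshold. Two investigators with the same laboratory report could reasonably differ on whether the next dose and the next EIA are forbidden. If the participant is stopped, the protocol then sends the investigator to monitoring instructions that do not cover the result.

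At stake are up to two further doses (Days 29 and 57) and the remaining EIAs, each with up to 56 g of ethanol for men or 48 g for women (Section 8.6.1). The drug acts in the liver, and safety is the primary objective.

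**Working it through.** The plan states no figure to reproduce. The check is to write each rule in Section 10.6 as a condition and see which ones are met.

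**Rules**

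| Rule | Aminotransferase part | Second part | Stated consequence |
|---|---|---|---|
| Box, line 1 | ALT or AST ≥3×ULN | none | listed as a stopping criterion |
| Box, line 2 | ALT or AST >2×ULN | bilirubin ≥2×ULN (>35% direct) or INR >1.5 | expedited report |
| Footnote a | ALT ≥3×ULN | bilirubin ≥2×ULN, fractionation unavailable | discontinue |
| Footnote b | ALT ≥3×ULN | bilirubin ≥2×ULN (>35% direct) or INR >1.5 | expedited report; SAE if criteria met |
| Monitoring tier 1 | ALT or AST ≥3×ULN | bilirubin ≥2×ULN or INR >1.5 | repeat within 24 hours, then twice weekly |
| Monitoring tier 2 | ALT or AST ≥3×ULN | bilirubin <2×ULN and INR ≤1.5 | tests within 24 to 72 hours, then weekly |
| Extended work-up | ALT or AST ≥3×ULN | bilirubin ≥2×ULN or INR >1.5 | added serology, imaging and/or biopsy |

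**Test profiles** (ALT and bilirubin in ×ULN; where bilirubin is 2.5, the direct fraction is assumed to exceed 35%; for footnote a, fractionation is taken as unavailable)

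| ALT | Bilirubin | INR | Line 1 | Line 2 | Fn a | Fn b | Tier 1 | Tier 2 | Extended |
|---|---|---|---|---|---|---|---|---|---|
| 2.5 | 2.5 | 1.0 | no | **yes** | no | no | no | no | no |
| 2.5 | 1.0 | 1.6 | no | **yes** | no | no | no | no | no |
| 2.5 | 1.0 | 1.0 | no | no | no | no | no | no | no |
| 3.0 | 2.5 | 1.0 | yes | yes | yes | yes | yes | no | yes |
| 3.0 | 1.0 | 1.0 | yes | no | no | no | no | yes | no |

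The first two rows are the problem. They meet line 2 and none of the other six rules. At 3.0×ULN the rules fit together.

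**Reading the passages for the first two rows**

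- *Must dosing and EIAs stop?* The box heading ("Applies both to additional DCR-AUD dosing and further EIAs"), the Actions row and Section 7.3.2 point to yes. Line 2's own sentence asks only for a report. Footnote a, attached to the same line, mentions discontinuation only from 3×ULN.
- *How is the participant monitored?* The Actions row defers to the tiers, and 0 of 2 tiers apply. The end point of monitoring is stated; its timing and frequency are not.

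**Two further signs of incomplete editing.** Footnote a is redundant as written, because line 1 already lists ALT ≥3×ULN whatever the bilirubin. The footnotes name ALT only, while the box, the tiers and the extended work-up name ALT or AST.

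**Distance from entry.** Inclusion criterion 5 requires AST, ALT, GGT and total bilirubin below 1.5×ULN. From just under that limit, 2.0 / 1.5 = 1.33, so a rise of about one third brings ALT or AST to 2×ULN. This covers only the aminotransferase half; line 2 also needs the bilirubin or INR part.

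**The case against.** The strongest reply is that the stopping reading is the natural one. The heading, Section 7.3.2 and the Actions row all support it, and an added duty to report does not cancel a stopping heading. Much of the work-up is then covered too: the Actions row and the base follow-up list (viral serology, CK, LDH, GGT, GLDH, albumin, blood count) have no aminotransferase threshold. Section 8.2.6 separately requires clinically significant abnormal results to be repeated until they normalise or stabilise. Section 7.3.2 also lets the investigator consider stopping for other abnormal liver tests, and under Section 9.6 the SRC may suspend dosing or EIAs at any time.

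Most of this stands and limits the point. A reader might infer that a participant in this band gets no repeat testing or work-up at all; the base list and Section 8.2.6 do not support that. A reader might also infer from footnote b that a result below 3×ULN need not be reported quickly. Footnote b says which events must be reported and does not exempt others, so line 2's instruction still stands. Nor is ALT 2.5×ULN with raised total bilirubin enough on its own to meet line 2: the direct fraction must exceed 35%, or INR must exceed 1.5.

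Two things remain unanswered. The investigator and SRC provisions are discretionary, so they do not settle whether stopping is mandatory. Neither they nor Section 8.2.6 supplies a monitoring schedule.

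Line 2 is also garbled in the text as read, with a stray inequality sign before its threshold. That may be an extraction fault, and nothing here relies on it.

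**Conclusion.** Section 10.6 is internally inconsistent. The affected band is ALT or AST above 2 and below 3×ULN with total bilirubin at or above 2×ULN (over 35% direct) or INR above 1.5. In it, one of the two box lines is met, but neither footnote, neither monitoring tier nor the extended work-up applies. Whether dosing and EIAs must stop depends on which sentence is followed, and the timing and frequency of monitoring are not set.

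The point does not extend to a claim that such a participant goes unreported or without follow-up. It rests on taking the 2×ULN threshold in the box as intended text. The documents give no basis for estimating how many of the 16 participants would fall in the band; both parts of the criterion must be met, so the consequence lies in the individual case, not in the study summaries. A correction before further dosing is worthwhile.

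**What to change.** Reconcile the 2×ULN and 3×ULN thresholds, and the analytes (ALT versus ALT or AST), across the Section 10.6 box, footnotes a and b, both monitoring tiers, the extended work-up and Section 7.3.2. State outright whether the combined line is a stopping condition for dosing and EIAs or a reporting condition only. Make sure every combination listed in the box maps to a monitoring tier. Which threshold or rule should prevail is for the sponsor to decide.

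The cost is a protocol wording change, mostly within one appendix section, with the IRB/IEC approval that Section 10.1.1 requires for amendments. It need not introduce any type of test that Section 10.6 does not already list.

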10.7. Abbreviations

Abbreviation	Description
ADA	antidrug antibody(ies)
AE	adverse event
AESI	AE of special interest
ALDH2	aldehyde dehydrogenase 2
ALDH2	gene for aldehyde dehydrogenase 2
ALP	alkaline phosphatase
ALT	alanine aminotransferase
AST	aspartate aminotransferase
AUC	area under the curve
AUD	alcohol use disorder
BAC	blood alcohol concentration
BMI	body mass index
BP	blood pressure
bpm	beats per minute
BUN	blood urea nitrogen
°C	degrees Celsius
CFR	Code of Federal Regulations
CFU	conditional follow-up
CIOMS	Council for International Organizations of Medical Sciences
CK	creatine kinase (creatine phosphokinase)
CL	clearance
C _{max}	maximum observed concentration
C _{min}	minimum observed concentration
CONSORT	Consolidated Standards of Reporting Trials
CRO	contract research organization
CSR	clinical study report
C-SSRS	Columbia-Suicide Severity Rating Scale
CTCAE	Common Terminology Criteria for Adverse Events
CV%	coefficient of variation (percent)
DCR-A1203	drug substance for this IMP

Abbreviation	Description
DS	drug substance
DSMC	Data Safety Monitoring Committee
ECG	electrocardiogram
eCRF	electronic case report form
e.g.	for example (exempli gratia)
EIA	ethanol interaction assessment
EOS	end of study
EOT	end of treatment
ETOH	ethyl alcohol
FDA	Food and Drug Administration
FIH	first-in-human
FSH	follicle stimulating hormone
GABA	gamma-aminobutyric acid
GalNAc	N -acetylgalactosamine
GCP	Good Clinical Practice
GGT	gamma glutamyl transferase
GI	gastrointestinal
GLP	Good Laboratory Practice
HbA1c	hemoglobin A1c
HBsAg	hepatitis B surface antigen
hCG	human chorionic gonadotropin
HCV	hepatitis C virus
HIPPA	Health Insurance Portability and Accountability Act
hr	hour(s)
HIV	human immunodeficiency virus
HRT	hormone replacement therapy
HV	healthy volunteer
IA	interim analysis
IB	Investigator's Brochure
ICF	informed consent form
ICH	The International Council for Harmonisation of Technical Requirements for Pharmaceuticals for Human Use

Abbreviation	Description
i.e.	that is (id est)
IEC	Independent Ethics Committee
IMP	Investigational Medicinal Product
INR	international normalized ratio
IRB	Institutional Review Board
ISR	injection site reaction
ITT	Intent to treat
IUD	intrauterine device
IVRS/IWRS	Interactive Voice/Web Response System
IUS	intrauterine hormone-releasing system
kg	kilogram(s)
LDH	lactate dehydrogenase
LFT	liver function test
MCH	mean corpuscular hemoglobin
MCHC	mean corpuscular hemoglobin concentration
MCV	mean corpuscular volume
mg	milligram(s)
min	minute(s)
MINI	Mini International Neuropsychiatric Interview
mL	milliliter(s)
mRNA	messenger ribonucleic acid
NOAEL	no observed adverse effect level
NPO	nothing by mouth
NSAID	nonsteroidal anti-inflammatory drug
OTC	over the counter
PD	pharmacodynamic(s)
PEth	phosphatidylethanol
PK	pharmacokinetic
PI	Principal Investigator
QTcF	QT interval (Fridericia correction)
RNA	ribonucleic acid
RNAi	RNA interference

Abbreviation	Description
SAE	serious adverse event
SAP	statistical analysis plan
SC	subcutaneous
SD	standard deviation
SIB	suicidal ideation or behavior
siRNA	small interfering RNA
SoA	schedule of activities
SRC	Safety Review Committee
SUD	substance abuse disorder
SUSAR	suspected unexpected serious adverse reaction
t _{1/2}	terminal elimination half-life
TBD	to be determined
TLFB	Timeline Follow Back
T _{max}	time to maximum observed concentration
ULN	upper limit of normal
UTI	urinary tract infection
Vd/F	apparent volume of distribution
WFI	water for injection
WOCBP	woman(en) of childbearing potential

10.8. Protocol Amendment History

Amendment 1 (17-Jan-2023)

Overall Rationale for the Amendment

The protocol was amended in response to queries from the US Food and Drug Administration. Additional updates and clarifications were also included.

The Protocol Amendment [Summary of Changes Table](#) for the current amendment is located directly before the Table of Contents.

List of Figures

Figure 3-1 Study Schematic for DCR AUD-102	12
--	----

Approved

REVISION HISTORY

Version No.	Effective Date	Summary of Change(s)
Final 1.0	28 Jun 2023	New document
Final 2.0	01 Sep 2023	Exploratory analysis updated

Approved

LIST OF ABBREVIATIONS

Abbreviation/Acronym	Definition/Expansion
ABE	Average bioequivalence
%AUC _{ex}	Percentage of AUC _{inf} obtained by extrapolation beyond t _{last}
ADA	Antidrug antibody
AE	Adverse event
ALDH2	Aldehyde dehydrogenase 2
ALDH2	Gene for aldehyde dehydrogenase 2
AESI	Adverse events of special interest
ATC	Anatomical Therapeutic Chemical
AUC	Area under the curve
AUC _{0-inf}	AUC from time zero extrapolated to infinity
AUC _{0-last}	AUC from time zero to the last quantifiable concentration
AUC _{0-t}	AUC from time zero to a specific time t
AUC _r	AUC over the dosing interval at steady state
B	Baseline
BDRM	Blinded data review meeting
BL	Biostatistician Lead
BLQ	Below the lower limit of quantification
BMI	Body mass index
BP	Blood pressure
bpm	Beats per minute
CI	Confidence interval
CL	Clearance
CL/F	Apparent clearance following extravascular (non-intravenous) administration, e.g., clearance following subcutaneous
C _{last}	Last quantifiable concentration at t _{last}
C _{max}	Maximum observed concentration
C _{min}	Minimum observed concentration at steady state
CPMS	Clinical Pharmacology, Modeling, and Simulation
CRF	Case Report Form
CS	Clinically significant
CSP	Clinical Study Protocol

Abbreviation/Acronym	Definition/Expansion
C _{trough}	Concentration at the end of a dosing interval [taken directly before next administration]
CTCAE	Common Terminology Criteria for Adverse Events
CV	Coefficient of variation
DBP	Diastolic blood pressure
DRM	Data Review Meeting
ECG	Electrocardiogram
ENR	Enrolled Analysis Set
EOS	End of study
ET	Early termination
HBsAg	Hepatitis B surface antigen
HCV	Hepatitis C virus
HIV	Human immunodeficiency virus
HR	Heart rate
GMR	Geometric mean ratio
IB	Investigator's Brochure
ICF	Informed consent form
IMP	Investigational medicinal product
LI	Linearity index
LLOQ	Lower limit of quantification
LOCF	Last observation carried forward
LOQ	Limit of quantification
MedDRA	Medical Dictionary for Regulatory Activities
mRNA	Messenger ribonucleic acid
MRT	Mean residence time
NA	Not available
NCS	Not clinically significant
NK	Not known
NR	Not reportable
NS	No sample
PCS	Potentially clinically significant
PD	Pharmacodynamic(s)
PDAS	Pharmacodynamic analysis set
PEth	Phosphatidylethanol

Abbreviation/Acronym	Definition/Expansion
PK	Pharmacokinetic(s)
PKP	Pharmacokinetic population
QTc	corrected QT interval
QTcB	QT corrected using Bazett's formula
QTcF	QT corrected using Fridericia's formula
R _{ac}	Accumulation ratio
SAE	Serious adverse event
SP	Safety population
SAP	Statistical Analysis Plan
SBP	Systolic blood pressure
SD	Standard deviation
SE	Standard error of the mean
SI	Standard international
SOC	System Organ Class
t _½	Apparent terminal elimination half-life
TEAE	Treatment-emergent adverse event
t _{last}	Time to last quantifiable concentration
t _{max}	Time corresponding to occurrence of C _{max}
V _{z/F}	Apparent volume of distribution during terminal phase following extravascular dosing
WHO-DD	World Health Organization - Drug Dictionary
λ _z	Terminal elimination rate constant

1 INTRODUCTION

This Statistical Analysis Plan (SAP) describes all planned analyses for the Clinical Study Report (CSR) of Study DCR AUD 102 A Phase 1b, Double-blind, Placebo-controlled, Repeat-dose, Safety, Tolerability, Pharmacokinetic, and Pharmacodynamic Study of DCR-AUD in Healthy Volunteers. This repeat-dose study is being conducted to characterize the safety and tolerability and PK profiles of DCR-AUD when administered monthly, and to determine if a PD effect (resulting from cumulative ALDH2 mRNA knock down) can be observed during Ethanol Interaction Assessments (EIA) in a population of social drinkers after repeat doses of DCR-AUD.

The content of this SAP is based on following study documents:

- Study DCR AUD 102 protocol Version 2.0 17 Jan 2023.
- Electronic Case Report Form (eCRF) Version 13.1.

This SAP will be finalized prior to database lock. Any changes after the finalization of this SAP will be documented in Statistical Method Modification Form.

